3.3.3.2 Definition of re-excisions

A re-excision is defined as a surgical procedure performed in the ipsilateral breast following the primary lumpectomy because of positive margins found from the initial lumpectomy procedure. The re-excision procedure can be a separate surgical procedure to excise further breast tissue or a mastectomy.

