15.1 Analysis Populations

- Safety (SAF) Population: the safety population includes all subjects who received study drug (LUM015).
- Modified Intent To Treat (mITT) population: includes the subjects in SAF, but excluding subjects who are not able to be imaged with the LUM Imaging System. The mITT population will be used as the primary analysis population for the three co-primary efficacy endpoints and efficacy analysis of the secondary endpoints.
- Per-Protocol Population: Includes mITT subjects who complete all study evaluations and are without any major protocol deviations that may impact data collection or efficacy analysis. A sensitivity analysis of the primary and secondary efficacy endpoints will be conducted using the per-protocol analysis set.

15.2 Definition of truth standard for diagnostic performance evaluation (sensitivity and specificity)

We propose to use a hierarchical approach to determine the truth standard as therapeutic shaves were taken only when the LUM imaging system signaled positive for potential residual tumor. The highest truth standard is whether pathology finds cancer in a tissue shave removed from the area that was imaged in the cavity. When a shave does not exist, then whether tumor is found in a re-excision surgery is considered as the truth standard. When neither a shave nor a second surgery exists for a given orientation that was imaged, the margin assessment of that orientation is used as truth standard. **Error! Reference source not found.** shows a schematic for determination of the truth standard.

LUMICELL CONFIDENTIAL

This document is confidential. Do not disclose or use except as authorized.

[figure not shown]

Figure 6: Definition of truth standard to evaluate the LUM Imaging System diagnostic performance.

When the therapeutic shave is not available and the follow-up surgery is performed, only the pathology from the first-time re-excision at the tissue/orientation level will be used for hierarchical sensitivity/specificity evaluation.

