3.2.2 Sensitivity and specificity

The instrument diagnostic accuracy is measured by sensitivity and specificity on a per-tissue basis. Because a LUM-guided shave does not exist when a negative LUM image is indicated we propose a hierarchical approach to determine the truth standard as depicted in Figure 2. The highest truth standard is whether pathology finds cancer in a tissue shave removed from the area that was imaged in the cavity. When a shave does not exist, then whether tumor is found in a re-excision surgery is considered as the truth standard. When neither a shave nor a second surgery exists for a given orientation that was imaged, the margin assessment of that orientation is used as truth standard. We believe that the hierarchical approach outlined to determine the truth standard is the most meaningful and practical assessment of device accuracy to predict the presence of cancer in the cavity.

LUMICELL CONFIDENTIAL

This document is confidential. Do not disclose or use except as authorized.

True positive = truth standard positive & Lum cavity image positive
 False negative = truth standard positive & Lum cavity image negative
 True negative = truth standard negative & Lum cavity image negative
 False positive = truth standard negative & Lum cavity image positive

Figure 2: Definition of truth standard to evaluate the LUM Imaging System diagnostic performance.

When a therapeutic shave and re-excision are not available for a given orientation, the margin from the prior resected tissue of the corresponding orientation will be used as ground inferred truth for evaluation (Figure 3). The number of prior positive margins contributing to the ground inferred truth for a patient will not exceed the number of orientations with positive margins.

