- f. Mean and median incremental volume (in cubic centimeters) of tissue removed from therapeutic shaves: For each patient, absolute shave volume will be calculated as length (c) × width (c) × depth (c) for each therapeutic shave with the sum by patient of all therapeutic shaves. Subjects with no therapeutic shaves taken will have a therapeutic shave volume of 0cc.

- g. Mean and median contribution of therapeutic shave volume to total tissue removed.

LUMICELL CONFIDENTIAL

This document is confidential. Do not disclose or use except as authorized.

- h. Average number of SOC and therapeutic shaves taken per subject overall and by type of SOC lumpectomy procedure (i.e., lumpectomy with comprehensive shaves vs. lumpectomy with or without selective shaves).
- i. Number of second surgeries recommended as a result of final positive margins.
- j. Rate of second surgeries as a result of a positive margin status following SOC (control arm) and LUM Imaging procedures (device arm).
- k. Rate of cancer found in second surgeries
- l. Number of second surgeries for each patient
- m. Number of images per subject from the cavity after SOC and first round of therapeutic shaves
- n. Secondary analysis of sensitivity and specificity including imaging before removal of SOC shaves.
- o. Number of device issues and malfunctions and their impact to data capture.
- p. Patient-level sensitivity and specificity
- q. Collect exploratory data on tissue types found in therapeutic shaves.
- r. Collect exploratory data on patient reported outcomes.
- s. Analysis of tissue-level sensitivity and specificity for the SOC procedure based on the outermost SOC resected surface.
- t. Adverse events stratified by severity and relatedness to drug/device.
- u. Serious adverse events stratified by severity and relatedness to drug/device
- v. Adverse events by preferred term (sorted by descending occurrences for each preferred term).
- w. Summary of adverse events, overall and split by expectedness to drug/device.
- x. Comparison of adverse events in subjects that have at least one therapeutic shave versus subjects that have no therapeutic shaves.

4 Statistical methods

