4.3.2 Performance goals

The verification of the sensitivity and specificity co-primary endpoints will be a refutation of the null hypotheses

$$H_{01}^s: sen \leq 40\% \text{ against the alternative } H_{11}^s: sen > 40\%$$

$$H_{02}^s: spec \leq 60\% \text{ against the alternative } H_{12}^s: spec > 60\%$$

where *sen* and *spec* represent the true sensitivity and specificity, respectively. The hypotheses involving sensitivity and specificity will be assessed based on the data collected per-tissue level.

These hypotheses will be tested using a one-sided significance level of 2.5%. To account for within-subject correlation, Generalized Estimating Equations (GEE), with a compound symmetry working correlation structure, will be used to estimate sensitivity and specificity along with an equi-tail 95% two-sided confidence interval (CI). The null hypothesis H_{01}^s is rejected if the lower bound of the confidence interval for sensitivity is larger than the performance goal of 40%. Similarly, the null hypothesis H_{02}^s is rejected if the lower bound of the confidence interval for specificity is larger than the performance goal of 60%.

Performance Goals selection for sensitivity and specificity endpoints

Data from the Phase C Feasibility Study showed pathology margin assessment sensitivity to predict cancer in the cavity of ~40%. However, this pathology assessment is done several days after the surgery and can lead to second surgeries. Because the LUM Imaging System provides the additional benefit of assessing the cavity in real-time, a performance goal for instrument sensitivity > 40% is proposed as the success criterion for this hypothesis-tested endpoint. We expect the sensitivity to be similar to that observed in the Phase C study of 69% [95% CI: 56%-80%].

LUMICELL CONFIDENTIAL

This document is confidential. Do not disclose or use except as authorized.

The Phase C data shows that at the current specificity performance of 70% [95% CI: 68%-73%], an average of 1.1 additional shaves were removed guided by the LUM Imaging system, accounting for ~10% of all the total resected tissue. We selected a performance goal for specificity of > 60% to ensure that similar performance in the pivotal trial is obtained regarding tissue removal. Also, with this lower bound, a Youden Index > 0 will be demonstrated to indicate non-random diagnostic performance.

Sample size for testing sensitivity:

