4.13 Exploratory Data Analyses

Patient reported outcome measures (PROMs) will be reported as an exploratory endpoint. Also, the type of tissue found in therapeutic shaves will be reported as an exploratory endpoint.

In this protocol, the definition of positive margins is described in section 3.2.2. In addition, Lumicell will collect margin distance information such that alternative definitions (e.g. DICS on ink) can be tested in an exploratory manner.

As an additional exploratory analysis, the sensitivity and specificity in a per-tissue basis for the outermost surface of the SOC procedure will be calculated with their respective 95% confidence interval. For this analysis, only tissue that has a subsequent therapeutic shave or second surgery will be included in the analysis.

5 References

1. Moran, M.S., et al., *Society of Surgical Oncology-American Society for Radiation Oncology consensus guideline on margins for breast-conserving surgery with whole-breast irradiation in stages I and II invasive breast cancer*. *Int J Radiat Oncol Biol Phys*, 2014. **88**(3): p. 553-64.
2. Morrow, M., et al., *Society of Surgical Oncology-American Society for Radiation Oncology-American Society of Clinical Oncology Consensus Guideline on Margins for Breast-Conserving Surgery With Whole-Breast Irradiation in Ductal Carcinoma In Situ*. *J Clin Oncol*, 2016.
3. Bartelink, H., et al., *Impact of a higher radiation dose on local control and survival in breast-conserving therapy of early breast cancer: 10-year results of the randomized boost versus no boost EORTC 22881-10882 trial*. *J Clin Oncol*, 2007. **25**(22): p. 3259-65.

LUMICELL CONFIDENTIAL

This document is confidential. Do not disclose or use except as authorized.

4. Levey, A.S., et al., *A new equation to estimate glomerular filtration rate*. Ann Intern Med, 2009. **150**(9): p. 604-12.

LUMICELL CONFIDENTIAL

This document is confidential. Do not disclose or use except as authorized.

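### SOC margin accuracy is computed only on tissue later shaved or re-excised, so SOC sensitivity is likely overstated and specificity understated, by an amount the documents do not fix

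*SAP*

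**What the plan says.** SAP 3.3 lists as secondary endpoint s: "Analysis of tissue-level sensitivity and specificity for the SOC procedure based on the outermost SOC resected surface". No restriction on the tissue is stated there. SAP 4.13 describes the same analysis, calls it exploratory, and limits the tissue: "For this analysis, only tissue that has a subsequent therapeutic shave or second surgery will be included in the analysis".

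Two other sets of rules decide which tissue qualifies.

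- **Therapeutic shave.** Protocol 15.2 says "therapeutic shaves were taken only when the LUM imaging system signaled positive for potential residual tumor". SAP 3.2.2 agrees: "Because a LUM-guided shave does not exist when a negative LUM image is indicated".
- **Second surgery.** Protocol 3.3.3.2 defines a re-excision as surgery performed "because of positive margins found from the initial lumpectomy procedure". Protocol 5.2.9.1 says that the outermost margin informs the decision. SAP 3.2.2 expects the re-excised orientation to be the margin-positive one, and assigns findings of unclear orientation to the margin-positive orientations.

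For tissue with neither, the truth standard in SAP 3.2.2 falls back on the margin itself. The SAP gives no caveat, no bounds and no count of excluded tissue for the SOC figures.

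**The concern.** This is partial verification that depends on the test being evaluated. Where LUM is negative no guided shave is indicated, so the final margin is still the SOC margin, and a positive one opens a second route to verification. Tissue negative on both tests is rarely verified. Cancers missed by both then drop out of the SOC sensitivity denominator, and cancer-free tissue negative on both drops out of the SOC specificity denominator.

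The extra route for margin-positive tissue drives the bias. Selection on LUM alone would leave SOC accuracy unbiased if the two tests were independent given cancer status; LUM's rates only scale the effect.

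At stake is what the trial can say about SOC pathology. Set beside LUM's own accuracy, which is computed on a wider set of tissue, the SOC figures would work against LUM on sensitivity and in its favour on specificity. They would also move if LUM's performance changed while SOC pathology did not.

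**Working it through.** **The plan's own figures.** The only SOC margin accuracy in the documents is the Phase C sensitivity of about 40% (SAP 4.3.2). It comes without counts, so it cannot be reproduced. The 4% truth-standard positive rate (SAP 4.3.2) does reproduce from SAP 4.5: 70/268 = 0.261 positives and 1021/152 = 6.717 negatives per patient, and 0.261/(0.261 + 6.717) = 3.7%.

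**Inputs**
- True SOC sensitivity s = 40%: the Phase C figure, taken as true for illustration.
- True SOC specificity c: not in the documents; assumed 95%, varied over 90% to 98%.
- LUM sensitivity: 67% (Protocol 15.3.2), 69% (SAP 4.3.2), 60% (design assumption).
- LUM specificity: 70% (Phase C).
- r = share of margin-positive, LUM-negative tissue verified by second surgery; q = the same share for double-negative tissue. The documents give neither, so both are varied.
- LUM and margin are independent given cancer status (assumption).

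**Formulas.** Let L be the probability that LUM is positive: its sensitivity in cancer tissue, or 1 − specificity in cancer-free tissue. The probability of verification is v₊ = L + (1 − L)r for margin-positive tissue and v₋ = L + (1 − L)q for margin-negative tissue.
- Planned sensitivity = s·v₊ / [s·v₊ + (1 − s)·v₋], with L = 0.67.
- Planned specificity = c·v₋ / [c·v₋ + (1 − c)·v₊], with L = 0.30.

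**Case 1: r = 1, q = 0**
- Sensitivity: 0.40 / (0.40 + 0.60 × 0.67) = 0.40/0.802 = 49.9%.
- Specificity: 0.95 × 0.30 / (0.285 + 0.05) = 85.1%.

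**Case 2: r = 0.5, q = 0.10**
- Sensitivity: v₊ = 0.835, v₋ = 0.703; 0.334 / (0.334 + 0.4218) = 44.2%.
- Specificity: v₊ = 0.65, v₋ = 0.37; 0.3515 / (0.3515 + 0.0325) = 91.5%.

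**Other inputs**

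| | r = 1, q = 0 | r = 0.5, q = 0.10 |
|---|---|---|
| Sensitivity (true 40%), LUM sensitivity 60 / 67 / 69% | 52.6 / 49.9 / 49.1% | 45.5 / 44.2 / 43.9% |
| Specificity, true value 90 / 95 / 98% | 73.0 / 85.1 / 93.6% | 83.7 / 91.5 / 96.5% |

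**Case 1 as counts per 1,000 tissues, 4% with cancer.** Of 40 cancers, 16 are margin-positive, 16.1 are margin-negative and LUM-positive, and 7.9 drop out: 16/32.1 = 49.9%. Of 960 cancer-free tissues, 48 are margin-positive, 273.6 are margin-negative and LUM-positive, and 638.4 drop out: 273.6/321.6 = 85.1%.

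**What bounds would show.** In the same example 7.9 + 638.4 = 646.3 tissues are unverified. Let their unknown cancer rate run from 0 to 4% (25.9 cancers). Sensitivity then runs from 16/32.1 = 50% down to 16/(32.1 + 25.9) = 28%. Specificity is (273.6 + 646.3)/967.9 = 95.0% at a rate of 0, and (273.6 + 620.5)/942.1 = 94.9% at 4%. Bounds can therefore nearly recover specificity, and they show how little is known about sensitivity.

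**Direction.** Under independence, sensitivity was overstated and specificity understated for every r of 0.5 or more with q of 0.10 or less. There is no bias if r = q. Sensitivity bias reverses if r = 0 with q above 0 (38.5% to 39.5% at q of 0.05 to 0.10), or under strong negative dependence given cancer with incomplete re-excision (37.9% at covariance −0.08, r = 0.5, q = 0). The selection rules point to neither.

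**Relative rates as an alternative.** The true ratios of LUM to margin are 0.67/0.40 = 1.68 for true positives and 0.30/0.05 = 6.0 for false positives. At r = 0.5, assuming all LUM-positive tissue is verified, they read 0.67/(0.40 × 0.835) = 2.01 and 0.30/(0.05 × 0.65) = 9.2. They need no double-negative tissue, but they do need near-complete verification of tissue positive on either test.

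**The case against.** The restriction has a good reason. For unverified tissue the hierarchical standard uses the margin as truth, so including it would score the margin against itself. SAP 4.13 states its inclusion rule openly, calls the analysis exploratory, and attaches no hypothesis, threshold or planned comparison with LUM. All of this stands, and it is why the remedy is a label with counts and bounds rather than a return to the hierarchical standard.

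Re-excision is also not automatic, nor is double-negative tissue never verified. Protocol 5.2.9.1 has the margin inform the surgeon's decision. Protocol 3.1 notes that clinical judgment applies to DCIS margins under 2 mm, which Protocol 3.3.3.1 counts as positive for pure DCIS. SAP 3.3 counts recommended and performed second surgeries separately, and SAP 3.2.2 lets a cancer-free mastectomy settle all orientations. Case 1 is therefore a limiting case; realistic verification shrinks the bias.

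A reader might take the illustration further and evaluate it at a LUM sensitivity of 40%, which gives 0.40/(1 − 0.6 × 0.6) = 62.5%. That is the null value; the documents' figures are 60%, 67% and 69%. A reader might also infer that the 40% performance goal rests on an SOC figure computed in this selective way. SAP 4.3.2 does not say how the Phase C value was obtained, so that link is unsupported. Finally, relative rates alone might look like a clean replacement. At 50% re-excision they are distorted too, and the true-positive ratio errs in the device's favour.

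**Conclusion.** The point holds as a matter of interpretation. As planned, the SOC figures describe accuracy among verified tissue, not the accuracy of the SOC margin. The likely direction follows from the plan's own selection rules: sensitivity too high, specificity too low. The size depends on r and q, which the documents do not give, on conditional independence, and for specificity on an assumed true value. Across the two verification patterns shown, with LUM at 67% and 70%, sensitivity is overstated by about 4 to 10 points from 40%, and specificity is understated by about 3 to 10 points from 95%. The co-primary tests and the 40% goal are not affected on anything the documents state. The change is still worth making, because it is cheap and because endpoint s, read alone, promises unconditional SOC accuracy.

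**What to change.** In SAP 4.13 and in endpoint s of SAP 3.3:

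1. Label the absolute SOC sensitivity and specificity as conditional on tissue with a later therapeutic shave or second surgery, and not as SOC accuracy. Put the restriction in both places.
2. Report the number of unverified tissues by margin result × LUM result.
3. Give bounds for SOC sensitivity and specificity over the unknown status of the unverified tissue, with the range of cancer rates stated in advance.
4. Add, as a supplement, the relative true-positive and false-positive rates of LUM versus margin, with intervals from a bootstrap by subject. State that they require near-complete verification of tissue positive on either test, and bound them for margin-positive tissue not re-excised and LUM-positive tissue not shaved.
5. State in both places whether the analysis is secondary or exploratory.

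The cost is SAP wording and one extra table from data already collected. An unconditional SOC sensitivity is no longer claimed.
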